Objective 2: Determine short-interval pregnancy, satisfaction, and continuation rates among women who received contraceptives in the home versus those that sought postpartum contraceptives through routine care.

Objective 3: Determine short-interval pregnancy, satisfaction, and continuation rates among women who opted for long-acting versus short-acting reversible contraceptives that were provided in the home setting.

Objective 4: Document side effects and adverse events occurring in the study population.

Methodology:

Study Design: This study is a cluster randomized trial of an intervention to increase uptake of postpartum contraception by providing them to women in their home and observe the effect on uptake in the community of interest. We have eight communities involved the healthcare services provides by the CHD that will be combined into six clusters, for study purposes. The clusters are independent of one another, except that some nurses offering the contraceptives may cover more than one cluster. Patients may also move between clusters over the course of the trial. Women will be recruited for enrollment into the CHD, and subsequently the study, blind to whether their cluster will be offered home-based contraception in the postpartum setting.

Operational Definitions/Proposed Intervention: This is a prospective community cluster-randomized study of a home-based intervention to increase uptake of postpartum contraceptives and study the direct effect on short-interval pregnancy, continuation, and satisfaction rates. The study has two phases.

Phase 1: The first phase fulfills AIM 1 and will involve a cluster randomized trial of the intervention, which is to bring and offer Jadelle[®], among all other routine postpartum contraceptive options, to the women in their homes, compared to routine care. Currently, around 4% of the population opts for Jadelle[®], which is less than expected, likely due to the fact that previously, Jadelle[®] was only offered

at a clinic inconvenient to the study population that required significant time and travel costs. Recently, implant availability has increased in the region due to the work of a non-governmental organization, and the nurses within the CHD were trained on implant placement. Therefore, Jadelle®, which was previously offered as part of the standard of care but not routinely available, now is accessible.

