Visit 1: At the postpartum visit in their home, patients will be enrolled in the study and provide informed consent. Once they have agreed to participate in the study, they will be offered postpartum contraception in the home in the intervention group, and through routine care (at CHD pharmacy or clinic location) in the control group. The nurses will bring all routinely available medications to the patient's home for those in the intervention clusters, including pills, condoms, Jadelle®, and depot medroxyprogesterone acetate. Patients who are breastfeeding will not be offered estrogen-containing methods. Participants in both the intervention group and control group will also be offered IUD placement; regardless of group, they will need to present to an area clinic setting for placement should they choose this method. Women opting for Jadelle® will receive immediate implant placement, and women that opt for other methods will receive their method of choice. 99% of patients in the community service program are seen for this postpartum visit, which is part of the standard of care for patients in this region.

Ninos Sanos Visits: The follow-up visits will occur through routine care as part of the Ninos Sanos program, into which all patients in the Madres Sanas program are automatically enrolled. Mothers are seen with their infants monthly in their home, including visits at six and twelve months after delivery. At these routine visits, the mothers enrolled in the study, in both groups, will complete a survey. The surveys will assess patient continuation rates and satisfaction with the contraceptive method of choice. Patients will also be queried about side effects such as: irregular bleeding, weight gain, headaches, rash, chest pain, moodiness, insertion site pain, cramps, acne, nausea, hair loss, or issues with breastfeeding after device placement. All patients will be questioned regarding repeat

pregnancy at these visits, as well, including outcomes of repeat pregnancies such as delivery, termination of pregnancy, or spontaneous abortion. We anticipate that this survey will take about 10 – 20 mins to administer. Additionally, the study nurses will perform a survey of their comfort and satisfaction with administering contraception in the home, which will be performed after enrollment is complete. These questionnaires are included with the submission.

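### Continuation is surveyed at fixed times after delivery, so any later method start in the control arm shortens time at risk and overstates control continuation relative to home provision

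*Combined protocol and SAP*

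**What the plan says.** All references are to the combined protocol and SAP.

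- **Comparison.** Research Objectives, Objective 2, concerns "satisfaction, and continuation rates among women who received contraceptives in the home versus those that sought postpartum contraceptives through routine care". As worded, the denominator is women who obtained a method, not all women enrolled.
- **Timing of measurement.** Under Ninos Sanos Visits: "Mothers are seen with their infants monthly in their home, including visits at six and twelve months after delivery". The same paragraph adds: "At these routine visits, the mothers enrolled in the study, in both groups, will complete a survey". On content it says: "The surveys will assess patient continuation rates and satisfaction with the contraceptive method of choice". Phase II and the Analysis Plan (Methods & Models) give the same two time points.
- **Where the method is obtained.** Under Study Visits, Visit 1, women are "offered postpartum contraception in the home in the intervention group, and through routine care (at CHD pharmacy or clinic location) in the control group". The same paragraph says "Women opting for Jadelle® will receive immediate implant placement". It also says that an IUD requires a clinic visit in either arm.
- **Analysis.** Programs Used lists t tests or non-parametric tests, chi-square or Fisher tests, bivariate group comparisons, and a logistic regression for repeat pregnancy. It gives no definition of continuation, no time origin and no time-to-event method.

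**The concern.** A continuation rate has a clear meaning only for a stated duration of use. Here the survey date is tied to delivery, while the date of first use can differ by arm because of the intervention itself. Both arms enrol at the same home visit. One is handed the method there, and the other has to make a trip. If control women start later, a control user at the six-month survey has used her method for less time than a home-arm user, and has had less opportunity to stop. With identical discontinuation behaviour in both arms, the tabulated percentages would still differ, in favour of routine care.

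At stake is the continuation part of Objective 2. This component of error runs against the intervention. Start dates that are not captured when they occur are also hard to recover later.

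**Working it through.** **The plan's own figure.** None is given for continuation. The only computed figure is power for implant uptake (3% v 15%, 100 per arm, two-sided 0.05), stated as 0.848. It reproduces: z = [0.12 − 1.96·√(2·0.09·0.91/100)] / √[(0.03·0.97 + 0.15·0.85)/100] = (0.12 − 0.0793)/0.0396 = 1.03, so power = 0.848. It does not bear on this point.

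**Inputs from the documents.** Surveys at t = 6 and 12 months after delivery; home-arm supply at the postpartum visit; control supply at a pharmacy or clinic.

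**Assumptions (no values in the documents).**
- Control delay d of 0.5 to 3 months, the same for every control user.
- True 12-month continuation S12 of 50% to 90%, equal in both arms.
- Constant discontinuation hazard.
- The short interval from delivery to the visit is ignored.

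**Formula.** With h = −ln(S12)/12, apparent continuation is exp(−h·t) in the home arm and exp(−h·(t − d)) in the control arm. There is no true difference, so the gap is wholly artefact.

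**Worked case.** S12 = 70%, d = 1 month, t = 6: home 0.70^(6/12) = 83.7%; control 0.70^(5/12) = 86.2%; excess 2.5 points.

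**Excess in the control arm, in percentage points:**

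| S12 | Survey | d = 0.5 | d = 1 | d = 2 | d = 3 |
|---|---|---|---|---|---|
| 50% | 6 mo | 2.1 | 4.2 | 8.7 | 13.4 |
| 50% | 12 mo | 1.5 | 3.0 | 6.1 | 9.5 |
| 70% | 6 mo | 1.3 | 2.5 | 5.1 | 7.8 |
| 70% | 12 mo | 1.0 | 2.1 | 4.3 | 6.5 |
| 90% | 6 mo | 0.4 | 0.8 | 1.7 | 2.5 |
| 90% | 12 mo | 0.4 | 0.8 | 1.6 | 2.4 |

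**Sensitivity to hazard shape.** With a falling hazard (Weibull, shape 0.7) the sign is unchanged. The excess at a 3-month delay runs from 1.7 to 11.6 points over the two surveys.

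**Measured from own start.** The artefact is 0 when the hazards are equal.

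**Method mix.** Assume 70% uptake of any method in both arms, the planned implant use of 15% v 3%, and 12-month continuation of 90% for implants and 60% for other methods. Implant shares among users are 0.15/0.70 = 21.4% and 0.03/0.70 = 4.3%. At twelve months:
- home: 0.214·0.90 + 0.786·0.60 = 66.4%
- control, no delay: 0.043·0.90 + 0.957·0.60 = 61.3%
- control, 1-month delay: 0.043·0.90^(11/12) + 0.957·0.60^(11/12) = 63.8%
- control, 3-month delay, by the same formula: 69.2%

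Control is overstated in both delayed cases, but is ahead only with the longer delay.

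**The case against.** The strongest reply is that the plan fixes when the survey is given, not how continuation will be calculated. The questionnaires were submitted separately and are not shown. Consent also covers registry, child-programme and medical-record data, so dates may well be collected. A reader might infer that start dates go unrecorded, but the documents do not support that. What stands is that the written analysis does not use such dates, whether or not they exist.

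Second, the length of the delay is unknown. The travel burden described under Phase 1 concerns past implant provision, and the same paragraph says the implant is now accessible. Both arms receive antepartum counselling and monthly home visits. The delay could be days, and the artefact then trivial. This is a fair limit on size but not on direction. The Background cites a home-dispensing trial with fewer uncovered days in the first 90 days after birth. That is consistent with earlier starts at home, but does not measure the delay here.

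Third, the effect is not universal. IUDs need a clinic visit in both arms, and abstinence, which the Background counts as a method, needs no trip.

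Fourth, continuation is one part of a secondary objective and will be imprecise. With an assumed 70 users per arm, 80% continuation and the plan's ICC of 0.02, the design effect is 1 + (70/3 − 1)·0.02 = 1.45. The standard error of the difference is √(2·0.16/70·1.45) = 0.081, about 8 points, so much of the range above lies within one standard error. This limits the consequence, but imprecision does not excuse a correctable bias.

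**Conclusion.** The concern holds as a bias component of known direction and unknown size. If continuation among users is tabulated at the two surveys, any positive delay in control starts overstates control continuation relative to the home arm, for methods other than the IUD. Under the stated assumptions the overstatement is 0.4 to 13.4 points at six months and 0.4 to 9.5 at twelve. It is small if the delay is short or continuation is high.

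Two stronger readings are not supported. A reader might infer that control women will come out as the better continuers, or that Objective 2 will be answered wrongly. The planned difference in implant use can outweigh the artefact, as the 66.4% v 63.8% case shows. A reader might also infer that a control woman who starts after six months counts as a continuer at the six-month survey. She is not yet a user, so she is outside that denominator and adds no bias there.

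The change is worth making because continuation is a named objective and the remedy is cheap.

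**What to change.** 1. Record each method's start date and its stop or removal date at the existing monthly visits or in the six- and twelve-month surveys, or confirm that the questionnaires already do so.
2. Define continuation as time from initiation to discontinuation. Report Kaplan-Meier estimates at 6 and 12 months of use, by method type, with late starters censored and variance allowing for the clusters.
3. Separately report the proportion of all enrolled women currently using a method at six and twelve months after delivery, as the comparison by randomized arm. Label it current use, not continuation.

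Item 3 keeps the randomized denominator, but it does not remove the dependence on start date. For example, assume 5% stopping per month, home start at month 1, control start 2 months later and 70% uptake in both arms. Current use at six months is then 0.70·0.95^5 = 54% at home and 0.70·0.95^3 = 60% in control. It reflects uptake, timing and discontinuation together, so it complements item 2 and does not replace it.

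The cost is two date fields and a revised definition, some recall error in the dates, and censoring of late starters before 12 months of use, because follow-up ends twelve months after delivery.

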continuation, satisfaction, and pregnancy rates. They will have the option to leave the study at any point without any repercussions for their clinical care. We will have these questionnaires performed in a private location, in a one-on-one setting to increase comfort with discussing these issues, and patients will also be able to complete the questionnaire privately if they are literate and do not need assistance.

The primary foreseeable risk of all parts of the study is a breach of privacy and/or confidentiality. Study data will be stored securely in REDCap, which is HIPAA compliant and controls access on a study-by-study basis through the use of unique usernames and passwords. REDCap allows data fields to be flagged as identifiers, and investigators will utilize this feature to remove identifiers from datasets, which are exported for analysis.

Utilization of postpartum contraceptives, including placement of the implant how contraceptive use affects short interval pregnancy rates are the specific aims of this study; the study cannot be performed without offering contraceptives, including device placement. Fortunately, these medications are already in use in the study population and are non-experimental methods. Therefore, with proper counseling and informed consent, we believe the risks of the procedure will be acceptable to the patients and their partners.

Analysis Plan:

Methods & Models: The primary outcome of this study is contraceptive uptake rates in the intervention group. This study, with 200 women enrolled (100 from intervention clusters and 100 from control clusters) will be powered to detect a change in Jadelle uptake rates from 3% to 15% at 85% power and 5% significance, with an intra class correlation of 2%.

The satisfaction surveys will be administered at the six and twelve month well-child visits and will primarily assess patient experience with the medications, including side effects, continuation rates, and pregnancy rates. This quantitative analysis will provide direct feedback in terms of real-world use of contraceptives, their success rates, and their acceptability to the patients, which will also provide baseline research for future interventions to address issues surrounding patient choice of and satisfaction with different method of contraception, including the implant.

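### Objective 2 compares continuation and satisfaction between groups formed by starting a method, so it cannot show the intervention's effect, and the bias could run either way

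*Combined protocol and SAP*

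**What the plan says.** Under Research Objectives, Objective 2 is to determine short-interval pregnancy, "satisfaction, and continuation rates among women who received contraceptives in the home versus those that sought postpartum contraceptives through routine care". The paragraph on Operational Definitions/Proposed Intervention says the trial will "study the direct effect on short-interval pregnancy, continuation, and satisfaction rates". The Analysis Plan (Methods & Models) states: "The primary outcome of this study is contraceptive uptake rates in the intervention group".

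Follow-up is described under Study Visits, Ninos Sanos Visits. At six and twelve months "the mothers enrolled in the study, in both groups, will complete a survey", and the section adds: "The surveys will assess patient continuation rates and satisfaction with the contraceptive method of choice". Repeat pregnancy is asked of every patient.

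The Analysis Plan gives no denominator for continuation or satisfaction. It names no outcome such as the share of all enrolled women using a method at six or twelve months, and it does not say that these outcomes are compared by assigned cluster. Programs Used says only that the groups will be compared by bivariate tests.

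**The concern.** Randomisation protects a comparison of women by the cluster they were assigned to. Objective 2, as worded, compares women by what they did afterwards: received a method at home, or sought one through routine care. A woman who starts nothing belongs to neither group. Under Visit 1, an intervention-cluster woman who chooses an IUD must go to a clinic, so she did not receive her method at home either.

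The primary outcome is uptake, so a successful intervention changes who becomes a user. Control users are those who obtained a method through routine care. Home users are comparable women plus those added by home supply. If the added women continue at a different rate, the user-only rates differ between arms even when home provision has no effect on continuation in anyone who would have started anyway. This would remain with perfect randomisation, complete follow-up and identical start dates.

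At stake is the promised direct effect on continuation and satisfaction. A difference between users could be an effect of home provision, a change in who the users are, or both, and the plan has no measure that separates them.

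**Working it through.** **The plan's own figure.** The only power figure concerns implant uptake: 3% v 15%, 100 women per group, two-sided alpha 0.05, power 0.848. Check, with mean proportion 0.09:

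- Null standard error: sqrt(2 × 0.09 × 0.91 / 100) = 0.0405
- Alternative standard error: sqrt((0.03 × 0.97 + 0.15 × 0.85) / 100) = 0.0396
- z = (0.12 - 1.96 × 0.0405) / 0.0396 = 1.03, giving power 0.848

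The figure reproduces, but it covers uptake only. The documents give no continuation rate, sample size or power for Objective 2 in this population, so what follows is an illustration.

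**Inputs.**
- uC and uI, the shares starting a method in control and intervention clusters. For the implant these are 3% and 15%, from the plan.
- cA, continuation in women who would start under either arm: 80%, assumed, and set equal in both arms so that any user-only difference comes purely from composition.
- cN, continuation in women who start only because of the home offer: 50% to 90%, assumed.
- No woman is assumed to start under routine care but not under the home offer.

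**Formulas.**
- Among users, control: cA
- Among users, intervention: (uC × cA + (uI - uC) × cN) / uI
- User-only difference: ((uI - uC) / uI) × (cN - cA)
- Among all enrolled women: share starting × continuation among users
- All-enrolled difference: (uI - uC) × cN

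**Implant, 3 v 15 per 100.** At cN = 50%, the intervention user rate is (3 × 0.80 + 12 × 0.50) / 15 = 8.4 / 15 = 56%.

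| cN | Users: control v intervention | Difference (points) | All enrolled: control v intervention |
|---|---|---|---|
| 50% | 80% v 56% | -24 | 2.4% v 8.4% |
| 60% | 80% v 64% | -16 | 2.4% v 9.6% |
| 70% | 80% v 72% | -8 | 2.4% v 10.8% |
| 80% | 80% v 80% | 0 | 2.4% v 12.0% |
| 90% | 80% v 88% | +8 | 2.4% v 13.2% |

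**Any method.** The plan gives no any-method uptake, so 50% v 70% is assumed, with the same continuation rates.
- Users, cN = 50%: (50 × 0.80 + 20 × 0.50) / 70 = 71.4% v 80%, or -8.6 points
- Users, cN = 90%: (50 × 0.80 + 20 × 0.90) / 70 = 82.9% v 80%, or +2.9 points
- All enrolled: 50% to 58% v 40%, or +10 to +18 points

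The sign of the user-only difference depends entirely on whether cN is below or above cA, which the documents do not tell us. The all-enrolled difference stays positive in this model whenever uptake rises and some added users continue.

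**The case against.** **Objective 2 may be loose wording for the two arms.** Visit 1 describes the arms in similar terms, the survey goes to mothers in both groups, and Objective 2 uses the same wording for pregnancy, which is asked of everyone. The survey sentence says what is measured, not who is compared. This stands in part. A reader might infer that the plan states a users-only analysis, but it does not. That reading is inferred from Objective 2 and from the absence of any other denominator. Even on the arm reading, though, continuation of a chosen method needs a rule for women who have none, and the plan gives no rule. Objective 3, listed next, is plainly a comparison of users: "among women who opted for long-acting versus short-acting reversible contraceptives that were provided in the home setting".

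**The direction is unknown.** A reader might infer that the home arm would show lower continuation because its extra users are less committed. The documents do not support that. Operational Definitions/Proposed Intervention attributes low implant use to an inconvenient clinic with time and travel costs, which is a barrier of access, not of motivation. Background describes long-acting methods as needing no user action and reports high continuation after postpartum placement in the cited study of adolescents. A shift towards implants could raise continuation among home users. This objection stands, and it is why the result is shown as a two-sided range.

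**The implant illustration rests on very few control users.** With three expected per 100, the planned tests would rarely declare either arm worse. That is true, but an imprecise comparison of non-comparable groups is still not an estimate of the intervention's effect.

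**Current use is not continuation.** It mixes uptake with persistence and gives satisfaction no randomised comparison. This stands as a cost of the remedy.

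**Conclusion.** The concern holds in this form: Objective 2 as worded compares groups formed after randomisation by an event the intervention is designed to change, and the plan defines no all-enrolled alternative. It cannot deliver the direct effect on continuation and satisfaction that the design paragraph promises.

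The size is illustrative. Composition alone moves the implant user-only difference by -24 to +8 points over the assumed range, and the any-method difference by -8.6 to +2.9. Only the 3% and 15% come from the plan. A finding that home provision makes continuation look worse is possible, not predicted.

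It would also be too strong to say that the data for an all-enrolled analysis are already secured. Every enrolled mother is surveyed, but the questionnaires are not in the text, so it cannot be verified that women who never started a method, or started late, are asked about current use.

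The primary uptake outcome is untouched. This is a change the sponsor should make to the secondary objectives.

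**What to change.** For Objective 2:

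1. Make the between-arm outcome the proportion of all enrolled women, by assigned cluster, who are using a method at six months and at twelve months. Count women who never started as not using.
2. Define which methods qualify. The end of Background counts abstinence among contraceptives, so say how it is classified.
3. Compare short-interval pregnancy by assigned cluster in all enrolled women as well.
4. Report continuation and satisfaction among users descriptively, by method, without a between-arm p-value.
5. Confirm that the six- and twelve-month questionnaires ask every enrolled woman about current method use, and add the question if they do not.

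The cost is analysis-plan wording and possibly one survey item, since every enrolled mother is already due to be surveyed. User-only continuation and satisfaction lose their status as formal arm comparisons, and current use combines uptake with persistence, so it should be labelled as such.

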Based on previously collected data, we expect that during our study timeframe around 260 women will meet eligibility criteria over the course of one year. The clusters will be randomly assigned by a biostatistician. This study, with 200 women enrolled (100 from intervention clusters and 100 from control clusters) will be powered to detect a change in Jadelle uptake rates from 3% to 15% at 85% power and 5% significance, with an intra class correlation of 2%.

[figure not shown]
Group	Proportion Positive	N Per Group	Standard Error	95% Lower	95% Upper
Population 1	0.03	100			
Population 2	0.15	100			
Rate Difference	-0.12	200	0.04	-0.20	-0.04

Alpha= 0.050, Tails= 2, Power = 0.848

Power computation: Normal approximation (unweighted mean p)
Precision computation: Log method

Phase II: Phase two of the study are six month and one-year follow-up visits that occur as part of routine care. Patients are immediately enrolled on delivery into Ninos Sanos, the early childhood health and development program offered through the CHD. Women and infants are seen monthly as part of the program, including routine visits at six and twelve months. At these sessions, mothers will be subject to a questionnaire regarding their contraceptive satisfaction and continuation habits, as well as whether or not they became pregnant since their delivery. This frequent and routine contact will ensure that patients are easily located for performing the follow-up questionnaire, but also will have no problem contacting study personnel if they have issues with their contraception or to report adverse events. We will also hold a focus group (interviews and surveys) for providers regarding their comfort and satisfaction with provision of care in the home setting before the study begins and after enrollment is complete.

Study Flow Diagram:

Study Visits: Patients who participate in the Community Health Services program through the CHD receive routine antepartum counseling on postpartum contraception in their home. At this visit, which is part of routine care, all women receive an educational intervention on contraception, which includes Jadelle® and the risks/side effects, benefits, and alternatives to the immediate postpartum implant.

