Unscheduled Visits: Unscheduled visits may occur if patients wish to be evaluated for side effects attributed to the implant or for implant removal.

Study Population: The study will be performed in the SW Trifinio region of Guatemala by the Center for Human Development (CHD), a partnership between Agro-America and the Center for Global Health (CGH) at the Colorado School of Public Health (CSPH). The study will be conducted within the current research infrastructure of the CHD and will involve assessments of patients at an antepartum visit, postpartum visit, and one year postpartum. Inclusion and exclusion criteria are outlined in the table to the right. No restrictions will be made based on pregnancy criteria; the only requirement is that patients be participants in the Madres Sanas community program offered by the CHD and already have been enrolled in the database.

Inclusion & Exclusion Criteria:

Inclusion Criteria:
1) Pregnant young women (age 15 – 35) in the CHD community health services program
Exclusion Criteria:
1) Active psychosis or altered mental status; must be able to provide informed consent
2) Unwilling or unable to participate in all study procedures

Procedures for Data Collection & Quality Control: The maternal community nursing program (Madres Sanas Program) that exists within the CHD focuses on improving prenatal care, screening pregnant women for complications, establishing a referral system for high-risk pregnancies, and shifting to facility delivery from home deliveries [6]. The Madres Sanas program uses a home visiting prenatal and newborn care model with community health nurses (CHN) who deliver four prenatal individual or group prenatal care visits, as well as an assessment of the mothers in their immediate postpartum periods [6].

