The same community health nurses who collect the database information and provide the clinical care will be trained in the consent, enrollment, and implant placement process for this study. During the postpartum visit, after a woman has completed her routine evaluation, the community health nurse will invite the woman to participate in this study. If she is not interested, it will not affect her involvement in the community program, she will receive care as usual. If she is interested, then the procedure for obtaining consent will be followed. While women can be enrolled in the clinical care database at any point during their pregnancy, the program entails four visits, ideally at <12 weeks, 13-28 weeks, 29-35 weeks, >36 weeks. During these visits information on health and pregnancy history are obtained as well as measurements of weight, fetal heart rate, fundal height, and blood pressure. Community health nurses come in contact with these women multiple ways: word of mouth, self-referral, referral through other CHD programs.

Procedures to Ensure Ethical Research: In order for the study to move forward as planned, it will require approval from numerous ethics organizations. These include the Colorado Multiple Institutional Review Board, the University Francisco Marroquin Institutional Review Board, and the Community Advisory Board for Research from the SW Trifinio region in Guatemala. These multiple levels of review will ensure that the research is culturally appropriate, that researchers are sufficiently qualified and expert to perform the proposed research, that the logistics of the international nature of the project are well planned and executed, and that dissemination of results back to the community is performed.

Patients are consented for this study at the postpartum visit. The patients participating in the cluster randomized trial will participate in a questionnaire at their six month and one year pediatric visits for the infant they delivered at enrollment into the study. Risks involved with the questionnaire are that patients may not want to answer questions about their contraceptive

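### Nurses who know the allocation invite and consent women after clusters are assigned, and the plan has nothing to prevent or reveal differential consent between arms

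*Combined protocol and SAP*

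**What the plan says.** All references are to the combined protocol and SAP.

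- **Allocation.** Phase 1 has a biostatistician assign the clusters at random. The Timeline shows three intervention and three routine-care clusters running through 2018.
- **Recruitment.** Under Visit 1, women are enrolled and consented at the postpartum home visit. Procedures for Data Collection & Quality Control has the community health nurse issue the invitation and adds that "The same community health nurses who collect the database information and provide the clinical care will be trained in the consent, enrollment" and implant placement.
- **Delivery.** Under Visit 1, the nurses bring the methods to the home in intervention clusters; control women obtain them through the CHD pharmacy or clinic. The offer follows agreement to take part. A woman who is not interested stays in the programme with her usual care.
- **Blinding.** Study Design says women are recruited "blind to whether their cluster will be offered home-based contraception in the postpartum setting". It makes no such statement about the nurses.
- **Eligibility.** Exclusion 2 reads "Unwilling or unable to participate in all study procedures".
- **Numbers.** Phase 1 expects that "around 260 women will meet eligibility criteria over the course of one year" and plans 200 enrolled, 100 per arm. The 99% figure under Visit 1 is attendance at the postpartum visit, not consent.
- **Analysis.** The primary outcome is contraceptive uptake; the power statement concerns implant uptake. The only regression described is for predictors of repeat pregnancy.

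**The concern.** Randomising clusters makes the eligible women in the two arms comparable apart from chance. It does not do the same for the women who consent, if consent comes after allocation and depends on something related to the outcome.

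Here a specific route exists. In intervention clusters, agreeing to take part is what leads to contraception at home. In control clusters it brings mainly questionnaires, with methods obtained where they would be anyway. A woman who already wants a method may therefore have a reason to consent in one arm that is absent in the other. The person inviting her knows the arm. No bad faith is needed.

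Uptake is a proportion of enrolled women, so under-enrolling women who want no method in one arm raises that arm's figure through the denominator. The plan does not say that every eligible woman is invited, does not commit to reporting eligible, invited and consenting women by cluster, and does not adjust the uptake comparison. A reader of the results could not separate this from an intervention effect.

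**Working it through.** **Order of events.** The date of allocation and the nurses' knowledge of it are not stated outright. Both follow from the text: the clusters run in fixed arms throughout the enrolment year, and a nurse carries supplies only where the cluster is allocated to the intervention.

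**The plan's own figure.** Inputs from Phase 1: 3% against 15%, 100 per arm, two-sided 5%.
- Null SE = √(2 × 0.09 × 0.91 / 100) = 0.0405
- Alternative SE = √(0.03 × 0.97 / 100 + 0.15 × 0.85 / 100) = 0.0396
- Power = Φ[(0.12 − 1.96 × 0.0405) / 0.0396] = 0.848, matching "Alpha= 0.050, Tails= 2, Power = 0.848".

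This reproduces without the intra-class correlation, which is a separate matter. It fixes the 12-point yardstick.

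**Assumptions for the bounds.** The 260 and 200 are the protocol's. Reading them as 130 eligible and 100 enrolled in each arm (200/260 = 77%, 30 not enrolled per arm) is an assumption. So is every any-method uptake below, because the documents give no baseline. The true uptake p among eligible women is equal in both arms, so any difference is spurious.

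**Extreme selection.** Highest enrolled uptake = min(130p, 100)/100; lowest = max(0, 130p − 30)/100.

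| True p | Intervention arm only | Opposite selection in both arms |
|---|---|---|
| 3% | 3.9% − 3% = 0.9 points | 3.9% − 0% = 3.9 points |
| 4% | 5.2% − 4% = 1.2 points | 5.2% − 0% = 5.2 points |
| 30% | 39% − 30% = 9 points | 39% − 9% = 30 points |
| 50% | 65% − 50% = 15 points | 65% − 35% = 30 points |
| 70% | 91% − 70% = 21 points | 91% − 61% = 30 points |

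The 3% is the planning rate; the 4% is the current implant share given elsewhere in the protocol.

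**Milder selection, intervention arm only.** Let q be the enrolment probability of would-be non-users and R the enrolment odds ratio for would-be users, so that q_u = R·o/(1 + R·o) with o = q/(1 − q). Solve p·q_u + (1 − p)·q = 100/130. Enrolled uptake is then p·q_u/(100/130).
- R = 2, p = 50%: q = 0.709, q_u = 0.830, enrolled uptake 53.9%, a spurious 3.9 points.
- R = 2 at other p: 0.4 points at 3%, 3.1 at 30%, 3.6 at 70%.
- R = 1.5, p = 50%: 2.3 points. R = 3, p = 50%: 6.1 points.

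**Effect on the test.** For R = 2, p = 50%: s = √(0.5 × 0.5/100 + 0.539 × 0.461/100) = 0.0706. The rejection rate is Φ(0.039/0.0706 − 1.96) + Φ(−0.039/0.0706 − 1.96), about 8.6% against a nominal 5%. For R = 3 it is about 13.8%. Clustering is ignored in both.

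**Inflation of a real effect.** If true implant uptake is 15% in the intervention arm and 3% in control, extreme selection in the intervention arm shows 130 × 0.15/100 = 19.5%. The difference becomes 19.5 − 3 = 16.5 points instead of 12.

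**The case against.** Several stronger readings are tempting, and the documents do not support them.

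- **That nurses choose whom to enrol.** The text says the nurse invites the woman, working from a prepared script; it grants no discretion. What stands is that no rule requires every eligible woman to be invited.
- **That 60 women are expected to refuse.** The protocol gives 260 eligible and a power calculation for 200 as separate statements. The gap could be refusal, a planning margin or a stop at 200. Under the last two, no selection need follow.
- **That exclusion 2 removes women who want no method.** The procedure is an offer, and women in both arms are offered contraception. Nothing says that declining makes a woman ineligible. The wording leaves this open, which is a reason to clarify it and not evidence of bias.
- **That blinding of the women must fail.** If maintained, it limits self-selection up to consent. The documents do not say whether the consent talk reveals the allocation. The blinding cannot cover the nurse.
- **That the bias is 15 points.** That figure needs an unsourced 50% baseline and every unenrolled intervention woman to be a non-user, with no selection in control.

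It is also fair to say that much of a consent log may already be derivable: participants are in the programme database and signed consents are uploaded to REDCap. What is missing is the commitment to record invitations and report by cluster.

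**Conclusion.** The concern holds in a limited form. Consent follows allocation, the recruiter knows the arm, consent carries a different consequence in each arm, and the plan neither prevents nor exposes the resulting selection.

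The size is unknown and depends on the outcome. For uptake of any method, the stated primary outcome, moderate selection (odds ratio 2, intervention arm only, assumed 50% uptake) gives about 3.9 points, and the extreme is 15. For implants at the planning rate of 3%, the ceiling is 0.9 points, or 3.9 with opposite selection in both arms. A reader might infer that selection could manufacture the implant result the trial is powered for. It cannot: under the assumed 130 eligible and 100 enrolled per arm, even the worst case falls well short of 12 points. It could, however, inflate a real effect. All of these figures rest on that assumed enrolment split.

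**What to change.** 1. In Procedures for Data Collection & Quality Control, state that every eligible woman visited is invited.
2. Log eligible, invited and consented women by cluster in the existing REDCap database, and report consent rates by arm.
3. Compare consenting women between arms on antenatal variables already collected. Adjust the uptake comparison for a few pre-specified ones, such as age and parity, and acknowledge that this only partly corrects selection on contraceptive intention.
4. State that declining a method, or the home offer, does not meet exclusion 2 in either arm.
5. Limit the blinding statement in Study Design to the women, up to consent.

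An uptake analysis over all eligible women is optional. Data access is described as part of consent, so it would need ethics approval. A record made at the visit could miss methods that control women obtain later at the pharmacy or clinic, so it is useful only if uptake is captured equally in both arms.

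The cost of items 1 to 5 is protocol wording, a short log and slightly more analysis.
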